The Clinical Study Protocol (CSP), Version 2.0, dated 07 Sep 2021, was updated with the following changes:

Section # and Name	Description of Change	Brief Rationale	Substantial/ Non-substantial
Synopsis, Safety Endpoints; Section 6.3.4 Ensuring Blinding; Section 6.3.5 Methods of Unblinding; Section 9.3 Populations for Analyses, Table 10; Section 9.4 Statistical Analyses; Section 9.4.1 General Considerations; Section 9.4.3.1 Safety Endpoint(s); Section 9.5 Interim Analyses	Language relating to primary and final database locks was added.	To add primary analysis of data at Visit 7 (Week 16).	Substantial
Section 1.3 Schedule of Activities, Table 2;	Footnote 'b' was added explaining procedures which are to occur at the investigational product discontinuation (IPD) visit.	To clarify that if the IPD or follow-up safety visit were to occur at the scheduled Visit 6 (Week 12) or Visit 7 (Week 16), that participants should have the flu vaccine and antibody assessments per Visit 6 (Week 12) and Visit 7 (Week 16).	Substantial
Section 2.2 Background	Updated to reflect new information based on Investigator's Brochure (IB) V 5.0	IB V5.0 has been updated to reflect new data from Phase 2 and Phase 3 asthma studies which have been reported.	Substantial
Section 2.2 Background; Section 11 References	CINQAERO Summary of Product Characteristics (SmPc) reference was updated to the current version.	The SmPc was updated in 2021.	Non-Substantial
Section 6.1.3 Medical Devices	Added section regarding sponsor manufactured medical device use in this study and all medical device deficiencies should be documented and reported by the investigator throughout the study	To align with International Organization for Standardization 14155 and European Medical Device Regulation	Substantial

Section # and Name	Description of Change	Brief Rationale	Substantial/ Non-substantial
Section 6.2.3 Reporting Product Complaints	Added section regarding any defects with IP that must be reported immediately to the AstraZeneca representative as per the Parexel study-specific Investigator Manual and defects will be investigated further with AstraZeneca.	To align with Parexel study-specific Investigator Manual.	Non-substantial
Section 6.2.4 Reporting Product Defects	Added section regarding product defects that should be reported to the AstraZeneca representative as per the study-specific Investigator Manual.	To align with Parexel study-specific Investigator Manual.	Non-substantial
Section 6.2.5 Single Use APFS device malfunction	Added section regarding Device malfunctions that should be reported using appropriate form as per the Parexel study-specific Investigator Manual.	To align with Parexel study-specific Investigator Manual.	Non-substantial
Section 7.1 Discontinuation of study Intervention	Language was added explaining procedures which are to occur at the investigational product discontinuation (IPD) visit.	To clarify that if the IPD or follow-up safety visit were to occur at the scheduled Visit 6 (Week 12) or Visit 7 (Week 16), that participants should have the flu vaccine and antibody assessments per Visit 6 (Week 12) or Visit 7 (Week 16).	Substantial
Section 7.1 Discontinuation of study Intervention	Language was added explaining procedures to be followed if the follow-up visit occurs on the same date as the scheduled Visit 7 (Week 16).	To clarify the procedures to be followed at the Follow-up visit.	Substantial
Section 8.1.2.5 Reversibility Test and Post-BD FEV1 Assessment	Second post-BD spirometry was updated to third post-BD spirometry.	Correction of an error.	Non-substantial

Section # and Name	Description of Change	Brief Rationale	Substantial/ Non-substantial
Section 8.3.12 Medical Device Deficiencies	Added Section 8.3.12 definitions of medical device deficiency and requirements to fulfil regulatory reporting obligations worldwide and investigator's responsibility for detection and documentation of events meeting the definition of device deficiency occur during the study.	To align with International Organization for Standardization 14155 and European Medical Device Regulation.	Substantial
Section 9.3 Populations for Analyses Table 10 and Table 11	Vaccine immunogenicity analysis set population updated to exclude participants who experience an influenza infection prior to Visit 7 (Week 16) assessments.	To reduce the potential to interfere with the generation or interpretation of an antibody response.	Substantial
Section 9.4 Statistical Analyses	Added wording to indicate selected safety objectives will be performed based on the primary database lock data.	To allow for review of selected safety outputs at primary database lock.	Non-substantial
Appendix D Actions Required in Cases of Increases in Liver Biochemistry and Evaluation of Hy's Law	Investigational Medicinal Product was updated to study intervention.	To align with other sections.	Non-substantial

1 PROTOCOL SUMMARY

1.1 Synopsis

Protocol Title: A Multicenter, Randomized, Double-blind, Parallel Group, Placebo-controlled, Phase 3b Study to Evaluate the Potential Effect of Tezepelumab on the Humoral Immune Response to Seasonal Quadrivalent Influenza Vaccination in Adolescent and Young Adult Participants with Moderate to Severe Asthma (VECTOR)

Short Title: Tezepelumab Humoral Immune Response to Influenza Vaccine Study

Rationale: The epithelial cell-derived cytokine, thymic stromal lymphopoietin (TSLP), is produced in response to proinflammatory stimuli and drives allergic inflammatory responses, primarily through its activity on type 2 innate lymphoid cells (ILC-2), dendritic and mast cells. Human TSLP expression is reported to be increased in asthmatic airways correlating with disease severity.

Owing to its immunomodulating effect, it is important to determine if tezepelumab affects functioning of the immune system. In this study, a functional response of the immune system will be assessed by measuring antibody responses to the influenza vaccine in adolescents and young adults with moderate to severe asthma.

The rationale for selecting this population is based on precedence from a similar study with anti-IL5 biologic drug benralizumab, in which humoral immune response was assessed in adolescents and young adults (12 to 21 years old) with severe asthma. In that study, the humoral antibody responses induced by seasonal influenza virus vaccination do not appear to be affected by benralizumab treatment.

Objectives and Endpoints

Please note: If influenza vaccine administration is delayed, some participants' assessments at Visit 6 (Week 12) and Visit 7 (Week 16) may be performed at later timepoints.

Objectives	Endpoints
Primary	

 To evaluate the effect of tezepelumab on the humoral immune response following seasonal influenza virus vaccination in adolescent and young adult participants with moderate to severe asthma 	
 Post-dose strain-specific hemagglutination-inhibition (HAI) antibody geometric mean fold rises (GMFRs) from Week 12 (pre-dose antibody measure) to Week 16 (EOT) Post-dose strain-specific microneutralization (MN) antibody GMFRs from Week 12 (pre-dose antibody measure) to Week 16 (EOT) Post-dose strain-specific serum HAI antibody geometric mean titers (GMTs) obtained at Week 16 (EOT) Post-dose strain-specific serum MN antibody GMTs obtained at Week 16 (EOT) Post-dose strain-specific antibody response at Week 16 (EOT) with antibody response defined as a \geq 4-fold rise in HAI antibody titer from Week 12 (pre-dose antibody measure) to Week 16 (EOT) Post-dose strain-specific antibody response at Week 16 (EOT) with antibody response defined as a \geq 4-fold rise in MN antibody titer from Week 12 (pre-antibody measure) to Week 16 (EOT) Post-dose strain-specific HAI antibody titer \geq 40 at Week 16 (EOT) Post-dose strain-specific MN antibody titer \geq 40 at Week 16 (EOT)
Secondary	

 To assess the PK and immunogenicity 	
 Serum trough tezepelumab concentrations Anti-drug antibodies
Safety	

 To assess the safety and tolerability of tezepelumab 	
 AEs and SAEs Laboratory variables Vital signs

For Exploratory objectives and endpoints, see Section 3 of the CSP.

Overall Design

This is a Phase 3b, multicenter, randomized, double-blind, parallel group, placebo-controlled study designed to investigate the potential effect of tezepelumab (210 mg SC Q4W) on antibody responses following seasonal quadrivalent influenza virus vaccination in the fall/winter 2021-2022 in the USA.

Disclosure Statement: This is a parallel group treatment study with 2 arms that is participant and investigator blinded. **Number of Participants:**

Approximately 135 participants aged 12 to 21 years with moderate to severe asthma will be enrolled into screening to provide a target sample size of approximately 100 randomized participants for the study.

Intervention Groups and Duration:

Participants with moderate to severe asthma will be randomized 1:1 to receive tezepelumab 210 mg or placebo SC Q4W, administered at Weeks 0, 4, 8 and 12. Enrollment into screening will be monitored to ensure at least 50% of the randomized participants are between the ages of 12 to 17 years. Treatment allocation will be stratified by age at the time of informed consent/assent (12 to 17 years, and 18 to 21 years) to ensure equitable distribution of tezepelumab and placebo treatment in each age group.

Please note: If influenza vaccine administration is delayed, the treatment period may be extended and therefore participants may be given an additional 1 to 2 study intervention doses (as needed) every 4 weeks for a longer period than initially planned.

Data Monitoring Committee: No

Statistical Methods

Primary Endpoints

For the analysis of the anti-influenza antibody response endpoints, GMFRs and GMTs for HAI and MN antibody measurements will be summarized by treatment group and by strain, and the least square geometric mean ratio of GMFRs and GMTs between treatment groups (influenza vaccine divided by tezepelumab and influenza vaccine) will be calculated via an ANCOVA model on the log-transformed variable, adjusting for treatment group and age stratum (adolescents aged 12 to 17 or young adults aged 18 to 21). The least square geometric mean ratio will be provided with associated 90% CI.

The antibody response to the quadrivalent influenza vaccine strain is defined as a ≥ 4 -fold rise in HAI or a ≥ 4 -fold rise in MN from pre-dose antibody measure to post-dose antibody measure. The proportion of participants who experience a post-dose antibody response at Week 16 (EOT) for HAI and the proportion of participants who experience a post-dose antibody response at Week 16 (EOT) for MN and corresponding 90% Clopper-Pearson exact CIs will be summarized by treatment group and by strain.

The proportion of participants who achieve a post-dose HAI antibody titer ≥ 40 and the proportion of participants who achieve a post-dose MN antibody titer ≥ 40 at Week 16 (EOT) and corresponding 90% Clopper-Pearson exact CIs will be summarized by treatment group and by strain.

Secondary Endpoints

Tezepelumab serum concentrations will be summarized using descriptive statistics at each visit. ADA to tezepelumab will be summarized using descriptive statistics at each visit.

Safety Endpoints

Adverse events will be coded using the Medical Dictionary for Regulatory Activities (MedDRA) version in force at the primary database lock. The definition of on-treatment and on-study for AE analyses will be given in the statistical analysis plan.

[figure not shown]
The number and percentage of participants with on-treatment and on-study AEs will be tabulated separately by preferred term and system organ class. An event that occurred one or more times during a period will contribute 1 observation to the numerator of the proportion. The denominator of the proportion will comprise all participants in the safety population. On-treatment AEs will also be summarized by intensity/severity and separately, by causality/relatedness (as determined by the investigator).

Laboratory data will be summarized by presenting shift tables using normal ranges (baseline to most extreme post-baseline value) and by presenting summary statistics of observed and change from baseline values (means, medians, quartiles, ranges). The incidence of clinically notable laboratory abnormalities will be summarized.

Vital signs data will be summarized by presenting summary statistics of observed and change from baseline values. The incidence of clinically notable vital signs abnormalities will be summarized.

1.2 Schema

Figure 1 Study Design

Abbreviations: n=number of participants.

1.3 Schedule of Activities

Table 1 Schedule of Activities (Screening)

Assessment/activity	Screening		Details in CSP Section or Appendix
Visit	V1 (Week -2 to -3)	V2 ^a (V1 plus maximum 7 days)	
Informed consent/assent	X		Section 5.1
Inclusion and exclusion criteria	X	X	Sections 5.1 and 5.2
Demography	X		Section 5.1
Medical and asthma history ^b	X		Section 5.1
Complete physical examination	X		Section 8.2.1
Weight, height, and BMI	X		Section 8.2.5.2
Vital signs	X	X	Section 8.2.2
Local 12-lead ECG	X		Section 8.2.3
Serum chemistry	X		Section 8.2.4
Hematology	X		Section 8.2.4
Local urinalysis	X		Section 8.2.4
Serum concentration (theophylline) ^c	X		Section 8.2.4
Serology (hepatitis B, C; HIV-1; HIV-2)	X		Section 8.2.5.3
Local SARS-CoV-2 viral diagnostic test ^d	X		Section 8.2.5.4
Serum pregnancy test ^e	X		Section 8.2.5.1
Pre-bronchodilator FEV ₁ ^f	X	X	Section 8.1.2.2
Post-bronchodilator FEV ₁ ^f	X	X	Section 8.1.2.3
Adverse Events	X	X	Section 8.3

Assessment/activity	Screening		Details in CSP Section or Appendix
	Visit	V1 (Week -2 to -3)	
Concomitant medication		X	X

^a Visit 1 and Visit 2 can be combined if the participant has the time and they have not taken SABAs for 6 hours or their long-acting bronchodilator-containing therapy for 12-24 hours. If spirometry/reversibility procedures are actually planned at Visit 1 as a convenience, then the ICF/assent must be signed prior to Visit 1 and prior to instructing the participant to withhold any medication.

^b To include influenza vaccination history.

^c For participants on theophylline, the serum concentration testing will be performed locally.

^d SARS-CoV-2 viral diagnostic test to be performed locally (local COVID-19 viral test).

^e For women of childbearing potential only.

^f Pre and post-bronchodilator spirometry can be done at Visit 1 OR Visit 2. If participants do not demonstrate airway reversibility at either Visit 1 or Visit 2 and this is needed to qualify the participant for randomization, the site should screen fail the participant.

Abbreviations: AE=adverse event; BMI=body mass index; CSP=clinical study protocol; COVID-19=Coronavirus disease 2019; ECG=electrocardiogram; FEV₁=forced expiratory volume in 1 second; HIV=human immunodeficiency virus; ICF=informed consent form; SABA=short-acting β-agonist; SARS-CoV-2= severe acute respiratory syndrome coronavirus 2; V=visit.

Table 2 Schedule of Activities (Randomization, Treatment, and Follow-up)

Assessment/activity	Treatment				Antibody response evaluation / EOT ^a	IPD ^b	FU / End of Study Visit	Unsch	Details in CSP Section or Appendix
Visit	V3	V4	V5	V6	V7		V8		
	W0	W4	W8	W12	W16		W28		
Visit window (days) ^c									
	± 0	± 3	± 3	± 3	± 3	± 3	± 3		
Inclusion and exclusion criteria	X								Sections 5.1 and 5.2
Randomization	X								Section 6.3.1
Complete physical examination	X				X	X	X		Section 8.2.1
Brief physical examination		X	X	X				X	Section 8.2.1
Vital signs	X	X	X	X	X	X	X	X	Section 8.2.2
CCI	█	█	█	█	█	█			
CCI	█	█	█	█	█	█	█	█	
Serum chemistry	X				X	X	X		Section 8.2.4
Hematology ^d	X				X	X	X		Section 8.2.4
Local urinalysis	X				X	X	X		Section 8.2.4
Urine pregnancy test (dipstick) ^e	X	X	X	X	X	X	X		Section 8.2.5.1
PK	X ^f			X ^f	X	X	X		Section 8.5.1
ADA	X ^f				X	X	X		Section 8.5.2
Serum antibodies to influenza virus				X ^g	X				
Administration of influenza vaccine ^h				X					Section 6.2.1.3
Administration of study intervention	X	X	X	X				X ⁱ	Section 6.2.1.3

Assessment/activity	Treatment				Antibody response evaluation / EOT ^a	IPD ^b	FU / End of Study Visit	Unsch	Details in CSP Section or Appendix
Visit	V3	V4	V5	V6	V7		V8		
	W0	W4	W8	W12	W16		W28		
Visit window (days) ^c									
	± 0	± 3	± 3	± 3	± 3	± 3	± 3		
Adverse Events	X	X	X	X	X	X	X	X	Section 8.3
Concomitant medication	X	X	X	X	X	X	X	X	Section 6.5

^a If influenza vaccine administration is delayed, unscheduled study intervention visits may occur prior to Visit 6 until the influenza vaccine is available at study sites. EOT assessments should be performed 4 weeks after last dose of study intervention.

^b If IPD visit occurs at the same time as the scheduled Visit 6 (Week 12), participants should perform all assessments, including influenza antibodies followed by influenza vaccination. Participants should then return to the study site for Visit 7 (Week 16) and perform all assessments, including influenza antibodies. Refer to CSP Section 7.1 for additional information.

^c All visits are to be scheduled from the date of randomization, not from the date of previous visit, except in the case of early discontinuation from study intervention (see Section 7.1 for details).

^d Eosinophils, basophil, and monocyte counts will be redacted from the central laboratory reports except at Visit 3 prior to study intervention administration.

^e For women of childbearing potential only, urine HCG test to be completed at study site on each study visit (before study intervention administration on Visit 3 to Visit 6).

^f PK and ADA to be collected PRIOR to study intervention dose at Visit 3 and PK to be collected PRIOR to influenza vaccination at Visit 6.

^g Blood draw for serum antibodies to influenza vaccine should occur prior to administration of influenza vaccine. If influenza vaccine administration is delayed from Visit 6 (Week 12), pre-influenza vaccine blood draw for serum antibodies should only occur on the week of influenza vaccine administration.

^h Influenza vaccine is to be administered at a different site than study intervention and site of injection noted. Participant is to be observed for 15 minutes after injection and before administering study intervention. Influenza vaccine is to be administered after scheduled blood samples are taken and prior to study intervention administration.

ⁱ If influenza vaccine administration is delayed, an additional 1 to 2 unscheduled study intervention visits may occur prior to Visit 6, until the influenza vaccine is available at study sites. All assessments during the unscheduled visit may not be necessarily completed.

Abbreviations: **CCI** ADA=anti-drug antibodies; AE=adverse event; CSP=clinical study protocol; EOT=end of treatment; FU=follow-up; HCG=human chorionic gonadotropin; IPD=investigational product discontinuation; PK=pharmacokinetics; Unsch=unscheduled; V=visit; W=week.

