3 OBJECTIVES AND ENDPOINTS

Please note: If influenza vaccine administration is delayed, some participants' assessments at Visit 6 (Week 12) and Visit 7 (Week 16) may be performed at later timepoints.

Table 3 Objectives and Endpoints

Objectives	Endpoints
Primary	

To evaluate the effect of tezepelumab on the humoral immune response following seasonal influenza virus vaccination in adolescent and young adult participants with moderate to severe asthma	
Post-dose strain-specific hemagglutination-inhibition (HAI) antibody geometric mean fold rises (GMFRs) from Week 12 (pre-dose antibody measure) to Week 16 (EOT)Post-dose strain-specific microneutralization (MN) antibody GMFRs from Week 12 (pre-dose antibody measure) to Week 16 (EOT)Post-dose strain-specific serum HAI antibody geometric mean titers (GMTs) obtained at Week 16 (EOT)Post-dose strain-specific serum MN antibody GMTs obtained at Week 16 (EOT)Post-dose strain-specific antibody response at Week 16 (EOT) with antibody response defined as a \geq 4-fold rise in HAI antibody titer from Week 12 (pre-dose antibody measure) to Week 16 (EOT)Post-dose strain-specific antibody response at Week 16 (EOT) with antibody response defined as a \geq 4-fold rise in MN antibody titer from Week 12 (pre-dose antibody measure) to Week 16 (EOT)Post-dose strain-specific HAI antibody titer \geq 40 at Week 16 (EOT)Post-dose strain-specific MN antibody titer \geq 40 at Week 16 (EOT)
Secondary	

To assess the PK and immunogenicity	
Serum trough tezepelumab concentrationsAnti-drug antibodies
Safety	

To assess the safety and tolerability of tezepelumab	
AEs and SAEsLaboratory variablesVital signs

Table 3 Objectives and Endpoints

Objectives	Endpoints
CCI	

Abbreviations: CCI

SAE=serious adverse events.

AEs=adverse events; PK=pharmacokinetic;

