The EOT Visit will be conducted at Week 16 and a final Follow-up Visit and the End of Study Visit will be conducted at Week 28.

Please note: If influenza vaccine administration is delayed, the treatment period may be extended and therefore participants may be given an additional 1 to 2 study intervention doses (as needed) every 4 weeks for a longer period than initially planned.

Participants will be maintained on their currently prescribed ICS-LABA therapies without

change from enrollment throughout the screening and treatment period. If asthma exacerbations occur during the treatment period, participants can be treated with oral or other systemic corticosteroids or other asthma therapies according to standard practice.

4.1.1 Study Conduct Mitigation During Study Disruptions Due to Cases of Civil Crisis, Natural Disaster, or Public Health Crisis

The guidance given below supersedes instructions provided elsewhere in this CSP and should be implemented only during cases of civil crisis, natural disaster, or public health crisis (eg, during quarantines and resulting site closures, regional travel restrictions, and considerations if site personnel or study participants become infected with SARS-CoV-2 or similar pandemic infection) which would prevent the conduct of study-related activities at study sites, thereby compromising the study site staff or the participant's ability to conduct the study. The investigator or designee should contact the study sponsor to discuss whether the mitigation plans below should be implemented.

To ensure continuity of the clinical study during a civil crisis, natural disaster, or public health crisis, changes may be implemented to ensure the safety of study participants, maintain compliance with Good Clinical Practice, and minimize risks to study integrity.

Where allowable by local health authorities, ethics committees, healthcare provider guidelines (eg, hospital policies) or local government, these changes may include the following options:

- Obtaining consent/reconsent for the mitigation procedures (note, in the case of verbal consent/reconsent, the ICF should be signed at the participant's next contact with the study site).
- Re-screening: One additional re-screening to confirm eligibility to participate in the clinical study can be performed in previously screened participants. The investigator should confirm this with the designated Parexel Medical Monitor.

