5.3 Lifestyle Considerations

Participants must abstain from donating blood and plasma from the time of informed consent/assent, and for 16 weeks (5 half-lives) after last dose of study intervention.

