6.6 Dose Modification

If influenza vaccine administration is delayed, an additional 1 to 2 unscheduled study intervention visits may occur prior to Visit 6 until the influenza vaccine is available at study sites.

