The participant should return for a Follow-up Visit 16 weeks (± 3 days) post last study intervention administration (refer to Section 1.3, SoA, V8 – Week 28). If the follow-up visit occurs on the same date as the scheduled Visit 7 (Week 16), all follow-up assessments should be performed, in addition to influenza antibodies.

See the SoA for data to be collected and for any further evaluations that need to be completed in case of discontinuation from study intervention.

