3.3.1 General Study Level Definitions

Unless stated otherwise, continuous variables will be summarized by descriptive statistics (number of participants [n], arithmetic mean, standard deviation (SD), minimum, median and maximum). Categorical variables will be summarized in frequency tables (frequencies and percentages).

Mean(s), median(s), SD(s) and quartiles (where applicable) will be displayed with one more decimal place than the collected data. Minimum(s) and maximum(s) will be displayed with the same number of decimal places as the collected data. For discrete variables, population size (N for analysis set size and n for available data) and percentage will be presented. Percentages will be displayed with one decimal place.

As no statistical testing is planned, no p-values will be presented.

If influenza vaccine administration is delayed, an additional one to two study intervention doses may be administered to participants during unscheduled visits prior to visit 6 (as needed) until the influenza vaccine is available at study sites. Throughout this document End of Treatment (EOT) refers to the end of treatment visit, which is four weeks after the last dose of study intervention and could be either week 16, 20 or 24 for each participant. The end of study visit is 16 weeks after last dose of study intervention.

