3.3.2 Visit Window

All summaries and analyses which are presented by visit will use the nominal visit label. This will allow for correct classification of Visit 6 (pre-vaccination antibody measure), Visit 7 (EOT), and Visit 8 (End of Study) at different time points for different participants due to influenza vaccination delay should it occur, as described in section [3.3.1](#).

Participants who discontinue study intervention early should attend all further study visits as defined in the CSP, hence any collected data will be used as planned.

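### Under vaccine delay the protocol moves Visits 6 and 7 but not Visit 8, so completers with extra doses could have 12 or 8 weeks of follow-up after last dose instead of the 16 the SAP assumes

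*Protocol*

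**What the plan says.** **Dosing under delay.** The planned doses are at Weeks 0, 4, 8 and 12. If the vaccine is late, Protocol 6.6 provides that "an additional 1 to 2 unscheduled study intervention visits may occur prior to Visit 6". Protocol 4.1 says the extra doses are 4-weekly.

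**Visits 6 and 7.** These have explicit delay text. Section 3 says that "assessments at Visit 6 (Week 12) and Visit 7 (Week 16) may be performed at later timepoints". Table 2 footnote a ties the EOT assessments to 4 weeks after the last dose, and footnotes g and i cover the pre-vaccination sample and the extra dosing visits.

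**Visit 8 in the protocol.** Table 2 footnote c says "All visits are to be scheduled from the date of randomization, not from the date of previous visit" and makes an exception only for early discontinuation. Section 4.1 says "a final Follow-up Visit and the End of Study Visit will be conducted at Week 28"; the delay note after it extends treatment without naming Visit 8. Section 7.1 has a rule tied to the last dose: "The participant should return for a Follow-up Visit 16 weeks (± 3 days) post last study intervention administration". That section concerns participants who stop study intervention.

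**Visit 8 in the SAP.** Section 3.3.1 states for all participants: "The end of study visit is 16 weeks after last dose of study intervention". Section 3.3.2 uses nominal visit labels so that it can handle "Visit 8 (End of Study) at different time points for different participants due to influenza vaccination delay". SAP Section 2, which lists changes from the protocol's planned analyses, does not mention this.

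**The concern.** For a delayed participant who completes treatment, the two documents give different dates for the final visit. Sites schedule from the protocol, and its only general rule points to Week 28. On that reading, the participants with the most doses have the shortest observation after the last one, shorter than someone who stopped early.

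The consequences would be:

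- **Adverse events.** The on-study AE period in SAP 4.6.2.1 runs to study completion, so it would cover unequal post-dose time.
- **PK, ADA and laboratory data.** Results are summarised by nominal visit, so Visit 8 would mix participants at different stages of washout.
- **Pregnancy testing.** Protocol 5.3.4 requires contraception for 16 weeks after the final dose, but the last scheduled pregnancy test is at Visit 8.
- **Prohibited medication.** Table 8 bars live vaccines, immunomodulators and other biologics until the Week 28 visit. That could be 8 weeks after a Week 20 dose.

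**Working it through.** **Inputs**

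- Last planned dose: Week 12 (Protocol 4.1).
- Extra doses under delay: k = 0, 1 or 2, every 4 weeks (Protocol 4.1, 6.6).
- EOT: 4 weeks after last dose (Table 2 footnote a). SAP 3.3.1 gives EOT at Week 16, 20 or 24, which matches k = 0, 1, 2.
- Visit 8 on the literal protocol reading: Week 28 (Protocol 4.1; Table 2 footnote c).
- Visit 8 on the SAP rule: last dose + 16 weeks (SAP 3.3.1).
- Washout: "for 16 weeks (5 half-lives) after last dose of study intervention" (Protocol 5.3), so one half-life = 16 / 5 = 3.2 weeks.
- On-treatment AE window: last dose + 33 days (SAP 4.6.2.1).

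**The plan's own figure.** Without delay, 28 − 12 = 16 weeks. Protocol 4.1, Protocol 7.1 and SAP 3.3.1 agree.

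**Formulas**

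- Last dose L = 12 + 4k; EOT = L + 4.
- Follow-up after last dose, literal reading: F = 28 − L weeks.
- Half-lives covered: F / 3.2.
- EOT to Visit 8: 28 − EOT weeks.
- Days observed beyond the on-treatment window: 7F − 33.
- Visit 8 under the SAP rule: L + 16.

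| | k = 0 (4 doses) | k = 1 (5 doses) | k = 2 (6 doses) |
|---|---|---|---|
| Last dose | Week 12 | Week 16 | Week 20 |
| EOT | Week 16 | Week 20 | Week 24 |
| Follow-up to Week 28 | 28 − 12 = 16 wk | 28 − 16 = 12 wk | 28 − 20 = 8 wk |
| Half-lives | 16 / 3.2 = 5 | 12 / 3.2 = 3.75 | 8 / 3.2 = 2.5 |
| EOT to Visit 8 | 28 − 16 = 12 wk | 28 − 20 = 8 wk | 28 − 24 = 4 wk |
| Days beyond +33 | 112 − 33 = 79 | 84 − 33 = 51 | 56 − 33 = 23 |
| Visit 8, SAP rule | Week 28 | Week 32 | Week 36 |

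Assuming first-order elimination, the fraction of the last-dose level left at Week 28 would be 0.5^5 ≈ 3%, 0.5^3.75 ≈ 7% and 0.5^2.5 ≈ 18%. All intervals are subject to the ± 3-day visit windows.

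Under the SAP rule, follow-up is 16 weeks and the time beyond the on-treatment window is 79 days in all three columns.

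**The case against.** The strongest reply is that footnote c cannot govern the delay case. Taken literally it would also freeze Visit 6 at Week 12 and Visit 7 at Week 16, and the protocol plainly moves both. Its contrast with the previous visit suggests it is meant to prevent drift within the planned schedule. Week numbers also serve as labels, since the protocol still writes Week 16 for a Visit 7 that can move. Section 7.1 shows where Week 28 comes from (Week 12 + 16) and names Visit 8 beside the 16-week rule, so the intention can be inferred. The Section 3 note introduces the endpoint table, which may explain why it names only Visits 6 and 7. The blood-donation and contraception periods run from the last dose, so a Week 28 visit does not shorten them, and suspected-related SAEs learned of after study end must still be reported.

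Much of this stands as evidence of intent. No passage expressly holds Visit 8 at Week 28 under delay, and the intended rule is probably 16 weeks after last dose. But Visits 6 and 7 have express text that overrides footnote c, and Visit 8 has none. The 16-week rule is written for discontinuers, and the SAP does not instruct sites. A site following the stated protocol rule would reach Week 28.

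**Conclusion.** The concern holds. For delayed completers the protocol, read literally, gives 12 weeks of follow-up after one extra dose and 8 after two, against 16 in the SAP. The Visit 8 dates differ by 4 or 8 weeks.

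This rests on three conditions: that vaccination is delayed, that extra doses are given, and that sites follow footnote c and Section 4.1 as written. The documents do not say how many participants were delayed; if none were, there is no effect. The 8-week figure is the worst case.

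The primary antibody endpoints and on-treatment AEs are unaffected, and no between-arm bias is claimed. What is affected is the completeness and comparability of on-study AEs and of the Visit 8 laboratory, pregnancy, PK and ADA data. That makes it worth correcting, but it does not threaten the trial's main result.

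**What to change.** In Table 2 footnotes a and c and in Protocol 4.1, state that when vaccination is delayed Visit 8 takes place 16 weeks (± 3 days) after the last dose: Week 28, 32 or 36 for zero, one or two extra doses. This extends the Section 7.1 rule to completers and matches SAP 3.3.1. Align the Week 28 wording in Table 8, Protocol 6.7, Protocol 9.4 and SAP 3.1.

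The cost is wording in two footnotes and a few matching lines. Delayed participants would have their final visit 4 or 8 weeks later. The final database lock could move by up to 8 weeks if the last participant is delayed; the change does not move the primary lock.
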